Treatment of type 1 diabetes mellitus (T1DM) requires daily insulin injections or use of an insulin pump, self-monitoring of blood glucose (SMBG) several times daily, regulation of carbohydrate intake, regular exercise and correction of hyperglycemia and hypoglycemia.³¹ The outcomes of family management of pediatric T1DM reflect many psychosocial influences.³²⁻³⁵ Some youths and families negotiate these challenges effectively, but others endure poorer glycemic control, treatment adherence, family relations and quality of life during this period.³²⁻³⁵ Poor adaptation to T1DM in youth may persist into early adulthood, increasing the risks of long-term complications.³⁶⁻³⁷ Practical methods are needed to enhance the capacity of youths and parents to manage T1DM effectively. Continuous glucose sensors (CGS) have now been developed that provide continuous real-time data on glucose levels and trends. The CGS could benefit many adolescents with T1DM by providing more useful feedback on glycemic levels, direction and variability than is feasible with conventional SMBG.³⁸⁻⁴³ But, these benefits may depend on how well families can collaborate in using CGS data for therapeutic decision-making.⁴⁴⁻⁴⁵ While youths in sub-optimal glycemic control could benefit from CGS, the benefits could be enhanced if they received a specific, targeted behavioral intervention. Drawing on our prior studies, the proposed research will explore whether glucose regulation by youths with T1DM using CGS can be enhanced by a behavioral intervention targeting diabetes management behaviors of adolescents and parents/caregivers that are critical to effective CGS use. This application addresses these specific aims:

SPECIFIC AIM 1. In a 3-center sample of 150 adolescents with T1DM and HbA_{1C} of 7.5% to 10.0%, we will compare the effects of Standard Care (SC) alone or augmented by either CGS alone (CGS) or CGS plus a behavior therapy intervention designed to optimize CGS benefits (CGS+BT). Primary outcome measures will be HbA_{1C}, 7-day continuous glucose profiles, and indices of blood glucose variability and risks for severe hypoglycemia. Frequency of severe and moderately severe hypoglycemia will be secondary outcomes.

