Glucose meter with memory All patients with T1DM at these clinics use glucose meters with memory, enabling storage of SMBG results by date and time. Downloading stored data provides a complete record of the patient's SMBG results. Patients will bring their meters to all clinic visits for downloading and discussion of treatment changes. Adolescents will receive a \$10 gift card at each clinic visit if they bring their blood glucose meters with them for downloading, a procedure that has yielded 94% adherence in the FMOD trial.

Downloaded data will yield descriptive statistics and measures of glycemic variability described below. The project will provide SMBG test strips to those without insurance coverage for them.

Continuous Glucose Sensor Diabetes Nurses will be trained by representatives of each CGS company, and with an on-line curriculum that will soon be on the JDRF website.¹⁴⁹ [name], R.N, a Diabetes Nurse in the JDRF Artificial Pancreas Project, will coordinate bi-weekly video-conferences for study nurses before enrollment and monthly case discussions in the first 2 years. Patients in the CGS and CGS+BT groups will select, with the help of diabetes nurses and physicians, the available CGS device that best matches their preferences for use during the study. The devices and supplies will be provided without charge. The same will apply to SC participants during the 3-month Continuation Phase. For the CGS and CGS+BT groups, a 7-day continuous sample of CGS data will be selected randomly from the months prior to the 3-month, 6-month and 9-month study visits to provide profiles for direct comparison to blinded CGS data for the SC group. Adolescents will be paid \$10 for downloading the CGS device and sending the data to the coordinating center monthly. In the DirecNet and JDRF studies, virtually all families have been able to arrange this using either their own computers or one owned by a relative, neighbor or employer. The study will provide a home computer, internet access and training for up to 15 low-SES families.

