Glycemic Variability Kovatchev's Low Blood Glucose Index (LBGI) and High Blood Glucose Index (HBGI) are derived from SMBG values¹⁰⁴⁻¹⁰⁸ and they reflect cumulative deviations of low and high glucose values from the logarithmic midpoint of the normal range. The LBGI and HBGI were validated as predictors of severe hypoglycemia and HbA_{1c}, respectively. The LBGI integrates the weighted values of each BG value that is below 112.5 mg/dl, the logarithmic midpoint of the normal range. The LBGI can be calculated over any interval ranging from a single SMBG result to multiple tests. The HBGI is calculated similarly from BG readings above 112.5 mg/dl. Kovatchev et al. have developed another metric derived from SMBG data, the Average Daily Risk Range (ADRR) and compared prediction of hypoglycemic and hyperglycemic events based on the ADRR with predictions from other indices of variability.¹⁰⁹ The ADRR was the best predictor of both hypoglycemic and hyperglycemic events. The proposed study will permit validation of the ADRR with children, which has not been done. Kovatchev et al. have also validated methods of quantifying glycemic variability for CGS data (Poincare Plots; blood glucose rate of change; Markov Chain interpretations) and these methods also warrant study in children.¹¹⁰⁻¹¹³ We will calculate all of these measures of glycemic variability quarterly from SMBG data (all groups) or CGS data (patients using CGS). For patients randomized to SC, we will calculate these indices based on the 7-day periods of blinded use of a CGS device at Baseline, 3-months, 6-months and 9-months. Comparisons of these measures as predictors of severe hypoglycemia will enable a direct comparison of the utility of SMBG and CGS for predicting those events. Kovatchev and colleagues have also shown that these indices are sensitive to changes in diabetes regimens such as initiation of pramlintide¹¹¹ and islet cell transplantation.¹¹² Kovatchev and Clarke¹¹²⁻¹¹³ have recently reported that the initial effect seen after adding CGS to T1DM therapy is reduced glycemic variability followed by decreased HbA_{1c}. The proposed study will examine whether similar effects occur in our sample during CGS use. [name] consultation provides added assurance that the substantial CGS data to be collected in this study will yield important contributions in the analysis of blood glucose dynamics and the validation of measures of glycemic variability.

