5.8. Procedures. Prior to randomization, all participants will complete the 7-day period of blinded CGS use. Data from the blinded CGS use will not be used for clinical management for the SC group. Participants who complete this run-in period will then complete the Baseline evaluation. Randomization will be stratified on Baseline HbA_{1c} ($\leq 8.8\%$ and $> 8.8\%$) and center. After the Baseline evaluation, the Diabetes Nurse will call the Project Coordinator at NCC-JAX to report the adolescent's HbA_{1c}. A randomization list will dictate the

adolescent's group assignment. The nurse will inform the family of their group assignment and then schedule an appointment with them for CGS training and with an endocrinologist to initiate intensive therapy.

The **Standard Care** regimen will have these features:

- Targets consisting of pre-prandial blood glucose of 70-120 mg/dl, 90 minute postprandial blood glucose below 180 mg/dl and 3AM blood glucose >65 mg/dl, unless the attending endocrinologist determines that a particular patient's risk of severe hypoglycemia requires revised targets.
- Targeted HbA_{1c} ≤ 7.0% unless the attending endocrinologist determines that a particular patient's risk of severe hypoglycemia requires revised targets.
- Targeted absence of severe hypoglycemic episodes and minimization of symptomatic hypoglycemia.
- Multiple daily subcutaneous insulin injections of a long acting (e.g. glargine) and short acting (e.g. Novalog or Humalog) insulin or continuous subcutaneous insulin infusion with an insulin pump. There will be enough patients using each type of insulin regimen to permit statistical comparisons between them.
- Completion of 4-6 blood glucose tests daily using a meter with memory function. Patients in all 3 groups will be instructed to use SMBG data to guide treatment decisions and insulin adjustments.
- Completion of a 3AM blood glucose test monthly using a meter (SC group only).
- Quarterly clinic visits with a Pediatric Endocrinologist.
- Monthly telephone consultation with a Diabetes Nurse.
- Advanced diabetes education regarding real-time and retrospective use of blood glucose data to minimize glycemic variability and optimize proportion of time spent in normoglycemia.
- Dietary management using carbohydrate counting with appropriate nutritional education and counseling.
- Referral for psychological services as needed based upon the opinion of the attending endocrinologist.

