- Incorporation of therapy advances that emerge before or during the study. The SC group may not use a CGS device during the 9-month randomization phase except in the blinded 7-day CGS use periods.
- *A "rescue procedure" will be employed for any youth whose HbA_{1c} remains above 9% for 2 consecutive visits or whose HbA_{1c} increases by more than 1.0% over baseline or who has more than one episode of severe hypoglycemia. As would typify clinical practices with similar patients, this will consist of offering monthly clinic visits with a diabetes nurse, weekly telephone consultation with the nurse and referral to a dietitian, social worker, psychologist or psychiatrist at the discretion of the treating endocrinologist.*

Patients randomized to SC will be treated as above but they will not use a CGS during the 9-month Randomized Phase. Given the enrollment criteria for this study, a baseline mean HbA_{1c} for this group can be expected to be about 8.8% and we anticipate a 0.2% increase (~0.15 SD) to about 9.0% during the 9-month randomization phase of the study.

All study participants will receive the above SC regimen. CGS and CGS+BT regimens will differ as below.

Continuous Glucose Sensor (CGS) With consultation from the diabetes team, patients randomized to CGS will select a CGS device for use during the study from among those that can be made available for use in this study. Appropriate training and counseling will be provided by the diabetes nurse to include:

- Parents and youths will be carefully trained in the safe and proper use of the selected CGS device and associated analytic software. *Substantial emphasis will be placed on making treatment decisions suggested by CGS results only after a confirmatory SMBG check is done. CGS use will be portrayed as a supplement to SMBG, not a replacement.* ¹⁴⁹ Training will cover real-time and retrospective analysis of CGS data and appropriate responses to alarms, using a book by H. [name]. ¹⁵⁰ and the JDRF website "Continuous Glucose Monitoring Classroom" that will soon be available for public access.
- Weekly phone contact initiated by the diabetes nurse during the first month of CGS use.
- 24-hour telephone access to an on-call pediatric endocrinologist.
- Week-day telephone access to the diabetes nurse to report device-related problems.

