8.4. Assessment of research-related risks: Risks of participation include those associated with using a CGS, those associated with management of diabetes mellitus with an intensive therapy approach, those associated with remaining in standard care for diabetes and those associated with threats to privacy and confidentiality. We believe that these represent minimal risks as defined by the DHHS Office of Human Research Protection and by the Policies and Procedures of the Nemours Office of Human Subjects Protection.

Risks associated with the various CGS's that will be evaluated consist primarily of irritation of the skin in the area on which the device is worn. This can manifest as an edematous rash that was rated as more than mild in about 10% of children who have worn these devices in previous DirecNet studies. This complication can be reduced or prevented by proper hygiene and skin care before and after wearing the device and by rotating the site on which it is worn from one period to the next.

A further risk associated with CGS's is the possibility that they will provide inaccurate data on prevailing glucose levels, potentially leading to inappropriate decisions with respect to insulin, eating or exercise. CGS education for adolescents and parents will instruct them to make no adjustments to insulin, food intake or exercise based on CGS data alone and to always confirm the CGS readings by performing a conventional SMBG test. Patient education on use of these devices will emphasize the necessity for healthy skepticism regarding the sensor data and the necessity of completing finger-stick blood glucose checks whenever the sensor readings do not appear congruent with recent trends or with treatment events such as insulin administration, eating or physical activity. These potential risks have not materialized in the European GuardControl Trial or in any of the DirecNet or JDRF studies of CGS devices that [name] has participated in. Most patients and parents have quickly learned that CGS results must be confirmed by conventional SMBG before treatment actions are taken.

Finally, adolescents who are non-compliant with their diabetes regimens may also be noncompliant with responsibilities and precautions associated with CGS use. Adolescents who do not calibrate the CGS properly, who ignore alarms, or who do not complete confirmatory SMBG checks when necessary may face risks of

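### Against Standard Care, Hypothesis 1's meter-derived variability indices depend on which fingersticks each treatment generates, so they can differ when glycemia does not

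*Combined protocol and SAP*

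**What the plan says.** Section 2, Specific Aim 1, counts "7-day continuous glucose profiles, and indices of blood glucose variability and risks for severe hypoglycemia" among the primary outcome measures, next to HbA1c. Hypothesis 1 (Sections 5.10 and 5.12) tests CGS+BT against both SC and CGS over the 9-month Randomized Phase on variability indices from two sources, meter and sensor.

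The meter source is the whole download. Section 5.5 states "Downloading stored data provides a complete record of the patient's SMBG results" and "Downloaded data will yield descriptive statistics and measures of glycemic variability described below". Under Glycemic Variability it adds: "We will calculate all of these measures of glycemic variability quarterly from SMBG data (all groups) or CGS data (patients using CGS". No rule says which meter readings count.

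The routine target is common to all arms: "Completion of 4-6 blood glucose tests daily using a meter with memory function". Two further kinds of fingerstick belong to sensor users only:

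- **Confirmatory checks.** Section 5.8 trains the CGS arms in "making treatment decisions suggested by CGS results only after a confirmatory SMBG check is done", and Section 8.4 has them "always confirm the CGS readings by performing a conventional SMBG test".
- **Calibration checks.** Section 3.3 says every device needs them.

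For SC, Section 5.8 says: "The SC group may not use a CGS device during the 9-month randomization phase except in the blinded 7-day CGS use periods".

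On frequency, Section 3.7 says fingerstick testing declined during sensor use in all the studies it cites. The Introduction reports no significant decline in one of them.

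**The concern.** An index computed from fingersticks describes the glucose values that happened to be tested. If treatment changes when and how often a youth tests, the index can change without any change in glucose. Randomization gives no protection, because the testing pattern changes after it.

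Section 5.12 reads a significant group difference in slope as due to the intervention program. Hypothesis 1 could thus be judged met or missed against SC on a meter index because of which readings were taken. The Hypoglycemia Diary text in Section 5.5 adds weight: if severe events are too rare to analyze, variability indices take their place, and it does not say from which source.

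**Working it through.** The plan gives no sample size, power or variance for these indices; Section 5.13 rests on HbA1c alone. There is no stated figure to reproduce, so the check asks whether the contrast can be non-zero with equal glycemia, and in which direction.

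**1. Indices that average a score over readings (LBGI, HBGI).** Let a youth take n routine checks a day with mean score R, and m further checks with mean score P. Then

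index = (nR + mP)/(n + m), so the shift is m/(n + m) × (P − R).

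This needs no glucose model. The routine target in Section 5.8 is 4 to 6 a day; n = 4 to 5 is used here, with m = 0.5 to 1 assumed:

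- Lowest share: 0.5/(5 + 0.5) = 9%.
- Highest share: 1/(4 + 1) = 20%.

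The sign is that of P − R. Checks prompted by low and high sensor values score above routine ones. Calibration checks made at unremarkable glucose can score below a routine record that already contains symptom-driven tests, and so dilute it.

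**2. Calibration load (Table 1).** Two devices need 2 checks a day. The third needs 4 per 120-hour sensor, or 4/5 = 0.8 a day, on a built-in meter. The plan does not say whether these fall within the 4 to 6 tests or whether the built-in meter's readings join the record.

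**3. ADRR.** The formula is not given. It is taken here as the daily maximum low risk plus the daily maximum high risk, averaged over days. Adding readings to a day cannot lower a maximum and removing them cannot raise it, so ADRR follows the number of readings, up or down.

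**4. Illustration with identical glucose traces.** Assumptions: 300 youths, 30 days, mean 180 mg/dL, CV 0.40, and a conventional log-based risk weighting whose zero falls at the plan's 112.5 mg/dL.

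| Meter readings | LBGI | HBGI | ADRR-like |
|---|---|---|---|
| 5 a day at random times (reference) | 0.46 | 10.53 | 25.25 |
| 3 a day at random times | 0.46 | 10.50 | 20.39 |
| 5 a day + checks at half of onsets <70 | 0.91 | 9.99 | 26.22 |
| 3 a day + checks at a quarter of onsets <70 and >250 | 0.72 | 13.31 | 25.91 |

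True glycemia is the same in every row. HBGI rises when high readings are confirmed too, and dips if only lows are. In a further set of assumptions, with a quarter of lows symptom-tested in both arms and two extra calibration checks a day, LBGI fell slightly. Only the signs are used here, because the sizes move with the assumptions.

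**5. Entry into the growth model.** No arm has open sensor use at baseline, so an artefact d follows the pattern 0, d, d, d at months 0, 3, 6, 9. The mean time is 4.5 and Sxx = 20.25 + 2.25 + 2.25 + 20.25 = 45. The slope is d(−1.5 + 1.5 + 4.5)/45 = 0.1d per month. The artefact therefore lands in the coefficient that carries the treatment effect.

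**6. Device range (secondary).** Table 1 gives 20–500 mg/dL for one device and 40–400 for two. Sections 5.5 and 5.16 let youths choose and switch devices, and no common range is set. Under the same weighting, risk is 57.0 at 400 and 79.1 at 500. One whole arm at 20–500 against another at 40–400, on the same traces (means 180 to 220, CV 0.40 to 0.50), changed LBGI by 0.001 (0.442 vs 0.441) to 0.009 (0.685 vs 0.676). HBGI changed by 0.171 (10.502 vs 10.331) to 0.802 (17.860 vs 17.058). A wider assumed glucose spread gave larger differences. The difference scales with the gap in device share and is zero if the arms use the same mix. Clipping at 40 and 400 does not change the proportion of values in the normal range.

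**The case against.** The strongest reply is that a sensor-based comparison with SC is already planned. Section 5.5 schedules blinded SC weeks for that purpose, computes SC indices from them, and gives the two sources a separate use: comparing meter and sensor as predictors of severe hypoglycemia. This stands, and it makes the remedy easy. It does not remove the meter-derived indices from Hypothesis 1 or say which source decides.

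Second, Section 5.8 tells all three groups to use meter data for treatment decisions, so SC checks are also tied to decisions. This narrows the difference between arms. It does not close it, since SC youths have no sensor to prompt a check.

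Third, the sensor-derived contrast has its own weakness: SC wear is blinded and CGS-arm wear is open. That is fair and must be stated as a limitation. But while worn, a sensor records at fixed intervals whatever the glucose value, so the selection shown above does not arise in the same form.

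Fourth, the substitute for severe hypoglycemia is not confined to meter indices, and Section 5.11 also plans a survival analysis of time to first event. A reader might infer that the hypoglycemia conclusion will rest on meter data; the documents only leave that open.

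A reader might also take Section 5.12 to claim that the indices are comparable between arms. It claims comparability across repeated measures, which is a different statement.

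**Conclusion.** The point holds for one set of contrasts: meter-derived variability indices against SC over months 0 to 9. As written, the plan can produce a difference there with identical glycemia and would attribute it to the intervention. The mechanism rests on the plan's own instructions and its use of the full meter record.

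The size is unknown. It depends on how many checks are prompted, whether routine testing falls, and how often lows are symptom-tested, none of which the documents give. A reader might infer that the artefact favors CGS+BT, or that it yields a definite false-positive rate. Neither is supported: prompted checks tend to raise HBGI, LBGI can move either way, and ADRR follows the reading count.

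Nor does the point reach HbA1c or its power. CGS+BT versus CGS is less exposed because both arms use sensors under the same instructions. The device-range issue is smaller: it matters for HBGI only if device mix differs by arm, hardly at all for LBGI, and not for the proportion in the normal range.

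**What to change.** (a) In Section 5.5 (Glycemic Variability), Hypothesis 1 in Section 5.10 and the matching text in Section 5.12, make the sensor-derived indices the inferential contrast with SC over months 0 to 9: SC blinded weeks against the CGS arms' 7-day samples. Report meter-derived indices against SC as descriptive or sensitivity results. If the substitute for severe hypoglycemia is invoked, use the sensor-derived indices. Meter-derived indices can stay for CGS versus CGS+BT and for the prediction work.

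(b) Before computing the indices, truncate all sensor values to the range common to the devices used, which is 40–400 mg/dL for those in Table 1.

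The cost is wording and one truncation step on data already planned, with no change to testing instructions. The meter contrast with SC loses inferential status, values beyond the common range are no longer told apart, and blinded versus open wear remains a stated limitation.

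As a drafting note only, align Sections 5.5, 5.7 and 5.8 on the sampling window (month or months before the visit) and on blinded wear: the Section 5.7 row is labeled for SC only even at month 0 and marks month 12, which Section 5.5 does not list.
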